7.4.1.2 Administration of IMP (Study Vaccine)

Serious allergic reactions including anaphylaxis may occur and for this reason subjects will be inoculated in a clinical area where Advanced Life Support trained physicians, equipment and drugs are im-

mediately available for the management of any serious adverse reactions. Participants will be observed for 24 h after vaccination. Subjects will be monitored and evaluated for AEs for at least 30 minutes after vaccination in attendance of an investigator.

7.4.1.3 Potential Benefits for Subjects

The vaccine recipients may benefit from protection against future MERS outbreaks. However, this trial is the first administrations of MVA-MERS-S vaccine to humans. Therefore, to date the risks-benefit ratio remains unknown. Participants will be strongly advised to not consider themselves protected against MERS after vaccination at this stage of vaccine development.

7.4.1.4 Summary of Potential Risks for Study Participants

In summary, preclinical data suggest a favorable safety and tolerability profile. An extensive body of relevant preclinical studies have been conducted that are needed to proceed to Phase I clinical testing. Although potential risks are known, such as Myo-/pericarditis, Vaccinia rash, eczema vaccinatum, Post-vaccinial encephalitis, so far clinical trials on MVA have reported transient and spontaneously resolved adverse events and no serious ones. Based on available information and the design of the study, the sponsor and the PI consider the trial to be ethically acceptable. The duration of confinement, the medical surveillance and the chosen time intervals for the sequential dosing of the first, second and third subjects of each dosing cohort are considered adequate to ensure maximal safety of the subjects and have been established with guidance of the competent authority. Thus, taking into account the safety measures to minimize risks for study participants, the exposure of healthy subjects with MVA-MERS-S vaccine is justified since the potential risks and disadvantages for study participants are outweighed by the potential benefits for medical research, medical practice and eventually for individuals at risk of MERS.

8 STUDY OBJECTIVES

8.1 Primary Objective

This study is designed to assess the overall tolerability and safety of two ascending doses of the experimental MVA-MERS-S vaccine (10^7 pfu and 10^8 pfu) administered to healthy subjects and to evaluate the reactogenicity after administration of two dosage levels of MVA-MERS-S. Subjects will be allocated to two different dose cohorts each receiving two vaccine injections, one at day 0 and another on day 28.

8.2 Primary Endpoints

The safety, tolerability, and reactogenicity of the experimental vaccine MVA-MERS-S will be measured as followed:

- Occurrence of solicited local reactogenicity signs and symptoms for 14 days following the vaccination (see Table 3)
- Occurrence of solicited systemic reactogenicity signs and symptoms for 14 days following the vaccination (see Table 4 and Table 5)
- Occurrence of unsolicited AEs for 28 days following the vaccination
- Change from baseline of safety laboratory measures
- Occurrence of SAEs throughout the study period

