17. History of blood donation within 60 days of enrollment or plans to donate within the treatment phase (until the 2nd vaccination).
18. Receipt of chronic (defined as more than 14 days) immune suppressants or other immune-modifying drugs within 6 months of study inclusion (screening).
 - For corticosteroids, this will mean prednisone, or equivalent, greater than or equal to 0.5 mg/kg/day.
 - Intranasal and inhaled steroids are allowed. Topical steroids are permitted provided they are not required to be applied to injection site.
19. Subjects with skin lesions close to the injection site or active oral lesions will be excluded.
20. Thrombocytopenia, contraindicating intramuscular vaccination based on investigator's judgment.
21. Subjects with a significant infection or known inflammation.
22. History of relevant cardiovascular disorders or evidence of hyper- (sitting blood pressure systolic >140 or diastolic >90 mmHg) or hypotension (sitting blood pressure systolic <90 or diastolic <40 mmHg) at screening.
23. Subjects who are known or suspected not to comply with the study directives.

24. Any other significant finding that in the opinion of the investigator would increase the risk of the individual having an adverse outcome from participating in this study.

Additional criteria for the subjects receiving the 3rd vaccination:

Receipt of any vaccine in the 2 weeks prior to (4 weeks for live vaccines) or 3 weeks following the 3rd vaccination.

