9.5.3.5.1 Adverse Events

The adverse events will be listed per subject using MedDRA terminology (preferred term and system organ class) and will be reported in tables summarizing the frequency of subjects with adverse events and adverse events by dosage level, by dose level and injection and by body system, the number of adverse events and number of subjects with adverse events by dosage level, by dosage level and injection, and the characteristics of adverse events.

For the hematology, clinical laboratory and the urine analysis deviations from the reference ranges will be summarized in frequency tables.

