9.7 Adverse Events

9.7.1 Definition of Adverse Events, Period of Observation, Recording of Adverse Events

An **Adverse Event (AE)** is any untoward medical occurrence in a clinical investigation subject administered an Investigational Medicinal Product (IMP) and that does not necessarily have a causal relationship with this treatment. An AE can therefore be any unfavorable and unintended sign (including an abnormal laboratory finding), symptom, disease or exacerbation of a pre-existing condition temporally associated with the use of a medicinal (test) product, whether or not considered related to the medicinal product (ICH Guidance E2A 1995).

All AEs, including those associated with the protocol, are collected from the time after first administration of IMP until the defined follow-up period and are to be recorded on the appropriate AE pages in the eCRF and in source documents. Where possible, a diagnosis rather than a list of symptoms should be recorded. If a diagnosis has not been made then each symptom should be listed individually.

A solicited AE is a predetermined event occurring within 14 days after application of IMP, which may reflect safety concerns related to the investigational product. The solicited AEs for this study include:

- Swelling, redness/ erythema, induration, hematoma or pain at site of injection
- Fever
- Chills
- Myalgia (described to the subject as generalized muscle aches)
- Arthralgia (described to the subject as generalized joint aches)
- Fatigue
- Headache
- Gastrointestinal symptoms (nausea, vomiting, abdominal pain, loose stool and/or diarrhea)
- Malaise

All AEs must be followed to closure (the subject's health has returned to his/her baseline status or all variables have returned to normal), an outcome is reached, stabilization (the investigator does not expect any further improvement or worsening of the event), or the event is otherwise explained regardless of whether the subject is still participating in the study. When appropriate, medical tests and examinations are performed so that resolution of event(s) can be documented.

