9.7.2 Severity Categorization of AEs

The severity of AEs must be recorded during the course of the event including the start and stop dates for each change in severity. An event that changes in severity should be captured as a new event. Worsening of pre-treatment events, after initiation of investigational medicinal product, must be recorded as new AEs.

The medical assessment of severity is determined by using the following definitions:

- Mild:** A type of AE that is usually transient and may require only minimal treatment or therapeutic intervention. The event does not generally interfere with usual activities of daily living.
- Moderate:** A type of AE that is usually alleviated with additional specific therapeutic intervention. The event interferes with usual activities of daily living, causing discomfort but poses no significant or permanent risk of harm to the research subject.
- Severe:** A type of AE that interrupts usual activities of daily living, or significantly affects clinical status, or may require intensive therapeutic intervention.

Additionally, the severity of AEs will be graded according to the toxicity scale described in section 9.7.11. If the AE is not defined in the tables of section 9.7.11 the severity will be graded according to NCI CTCAE (current version).

The severity assessment is described more detailed in section 9.7.11.

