Hypertension**	Prehypertension (systolic BP 120-139 mmHg or diastolic BP 80-89 mmHg)	Stage 1 hypertension (systolic BP 140-159 mmHg or diastolic BP 90-99 mmHg); medical intervention indicated; recurrent or persistent (≥24 h); symptomatic increase by >20 mmHg (diastolic) or to >140/90 mmHg if previously within normal limits; monotherapy indicated	Stage 2 hypertension (systolic BP ≥160 mmHg or diastolic BP ≥100 mmHg); medical intervention indicated; more than one drug or more intensive therapy than previously used indicated	Life-threatening consequences (e.g., malignant hypertension, transient or permanent neurologic deficit, hypertensive crisis); urgent intervention indicated	Death
Hypotension	Asymptomatic, intervention not indicated	Non-urgent medical intervention indicated	Medical intervention or hospitalization indicated	Life-threatening and urgent intervention indicated	Death

Definitions

Fever	A disorder characterized by elevation of the body's temperature above the upper limit of normal.
Tachycardia	A disorder characterized by a dysrhythmia with a heart rate greater than 100 beats per minute.
Bradycardia	A disorder characterized by a dysrhythmia with a heart rate less than 60 beats per minute.
Hypertension	A disorder characterized by a pathological increase in blood pressure; a repeatedly elevation in the blood pressure exceeding 140 over 90 mmHg.
Hypotension	A disorder characterized by a blood pressure that is below the normal expected for an individual in a given environment.

*Taken after ≥10 minutes at rest; **when resting heart rate is between 60–100 beats per minute. Use clinical judgement when characterizing bradycardia among some healthy subjects, for example, conditioned athletes. From CTCAE v4 (http://evs.nci.nih.gov/ftp1/CTCAE/CTCAE_4.03_2010-06-14_QuickReference_5x7.pdf)

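### The primary solicited systemic endpoint points to Tables 4 and 5, whose items differ from the solicited AE list in 9.7.1, and Table 4's Grade 1 hypertension band contradicts the definition printed beneath it

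*Protocol*

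**What the plan says.** - **Endpoint (8.2).** The solicited systemic endpoint reads "Occurrence of solicited systemic reactogenicity signs and symptoms for 14 days following the vaccination (see Table 4 and Table 5". Table 4 covers fever, tachycardia, bradycardia, hypertension and hypotension. Table 5 covers headache, fatigue, myalgia, arthralgia, chills, sweats, subjective fever, nausea, vomiting, abdominal pain, diarrhea and an open row for other systemic symptoms. A separate primary endpoint counts unsolicited AEs for 28 days.
- **Solicited list (9.7.1).** "A solicited AE is a predetermined event occurring within 14 days after application of IMP, which may reflect safety concerns related to the investigational product". Listed items are injection-site swelling, redness, induration, hematoma and pain; fever; chills; myalgia; arthralgia; fatigue; headache; gastrointestinal symptoms; and malaise.
- **Holding rules (9.3.3.3).** Physical observations of Grade 3 or higher are attached to the solicited systemic rule and are also named as part of the unsolicited rule.
- **Blood pressure (9.7.11.2, Table 4).** Grade 1 hypertension is "Prehypertension (systolic BP 120-139 mmHg or diastolic BP 80-89 mmHg"). The definition under the same table is "a repeatedly elevation in the blood pressure exceeding 140 over 90 mmHg". Exclusion criterion 22 removes only "sitting blood pressure systolic >140 or diastolic >90 mmHg" at the upper end.
- **Recording and tabulation.** Section 9.7.2 states "An event that changes in severity should be captured as a new event". Section 9.5.3.5.1 tabulates "the number of adverse events and number of subjects with adverse events by dosage level".
- **Analysis.** Sections 9.8.1.3 and 9.8.2 plan descriptive summaries by dose level in 24 subjects, 12 per dose. No expected rate of solicited reactions is given.

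**The concern.** In a descriptive first-in-human trial with 12 subjects per dose level, the observed frequencies of solicited and unsolicited events are the primary result. Two sections of the protocol give different answers to which events are solicited.

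This goes beyond detail that can wait for a statistical analysis plan. A plan that follows 8.2 as written departs from 9.7.1, and one that follows 9.7.1 departs from the tables that 8.2 names.

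The blood-pressure row makes the choice matter more. Its lowest grade covers readings with which a subject may enter the trial. If such readings entered the solicited endpoint, background blood pressure would contribute to a reported reactogenicity rate.

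**Working it through.** **1. The two lists side by side**

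| Item | Tables cited in 8.2 | List in 9.7.1 |
|---|---|---|
| Fever, chills, myalgia, arthralgia, fatigue, headache, gastrointestinal symptoms | yes | yes |
| Tachycardia, bradycardia, hypertension, hypotension | Table 4 | no |
| Sweats, subjective fever | Table 5 | no |
| Malaise | only under *Other systemic symptoms* in Table 5 | yes |
| Hematoma (local) | no row in Table 3 | yes |

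The open row in Table 5 cannot itself be a solicited item, because 9.7.1 requires the event to be predetermined.

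Take sweats on day 10 after an injection. Read through 8.2 and Table 5, this is a solicited systemic event. Read through 9.7.1, it is unsolicited. It moves from one primary endpoint to another.

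Section 9.3.3.3 does not settle the matter, since physical observations appear under both rules. The two rules also count differently. The solicited rule counts injections and sets an onset window. The unsolicited rule counts subjects and requires probable or definite relatedness.

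**2. The Table 4 hypertension row**

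Grade 1 is 120–139 systolic or 80–89 diastolic. Entry is refused only above 140 or above 90, so the whole Grade 1 band is admissible. The definition below the table requires repeated values above 140/90, which no reading within the Grade 1 band can meet.

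**3. Size under the literal reading**

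The protocol states no rate, so there is no figure to reproduce beyond 12 + 12 = 24.

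Scheduled post-dose readings within 14 days:
- Dose 1: 2, 4, 6, 8, 12 and 24 h, then days 3, 7 and 14, so 6 + 3 = 9.
- Dose 2: the same six, then days 35 and 42, so 6 + 2 = 8.
- Both doses: 9 + 8 = 17.

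*Independent readings.* With chance p that one reading is at least 120 or at least 80, the chance of at least one such reading in k is 1 − (1 − p)^k:

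| p | k = 9 | k = 17 |
|---|---|---|
| 0.05 | 0.37 | 0.58 |
| 0.10 | 0.61 | 0.83 |
| 0.20 | 0.87 | 0.98 |
| 0.30 | 0.96 | 0.998 |

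If readings were fully correlated within a subject, the answer would be p itself, so the truth lies between.

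*Simulation with within-subject correlation.* The assumptions, none of them from the protocol, are between-subject SD 10/8 mmHg, within-subject SD 5/4 or 8/6, systolic–diastolic correlation 0.6 and no vaccine effect. There were 200,000 simulated subjects per setting, restricted to those whose screening reading passes criterion 22. Each range below runs over the two within-subject SDs.

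| Assumed mean (mmHg) | Pre-dose reading in band or above | Any of 9 post-dose readings in band or above | In band or above only after dosing | At least 2 of 9 above 140 or 90 |
|---|---|---|---|---|
| 112/68 | 27–30% | 53–71% | 28–42% | 2–4% |
| 115/72 | 37–40% | 66–80% | 30–42% | 4–8% |
| 120/75 | 53% | 80–90% | 29–38% | 8–15% |
| 125/78 | 66–68% | 90–95% | 23–30% | 14–26% |

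The literal reading flags 53–95% of eligible subjects after dose 1. Counting only subjects whose pre-dose reading was below 120/80 flags 23–42%. The printed definition, taken as at least two of nine readings, flags 2–26%. With the 9.7.1 list, blood pressure adds 0%, because it is not on that list.

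**4. Event counts**

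Under 9.7.2 a reaction that runs mild, moderate, mild is three records. It remains one subject with that event.

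**The case against.** The best defence is that Tables 3–5 are titled as grading scales and introduced as scales for assessing severity, so the pointer in 8.2 is only a pointer to grading. Section 9.7.1 states what is solicited and contains no blood-pressure or heart-rate item, and the diary in 9.5.2.8.9 asks for temperature and solicited reactions. This is the more natural reading, but it does not remove the conflict. Section 8.2 attaches the tables to the occurrence of events and does not cite 9.7.1, and 9.3.3.3 links physical observations to the solicited rule.

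Several stronger inferences are tempting, and the document does not support them:

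- *The solicited rate will approach 100%.* This needs Table 4 used as an event list, every single reading counted, and a high assumed blood pressure. Section 9.7.2 makes a pre-treatment condition a new AE only when it worsens, and the definition under Table 4 asks for repeated values above 140/90.
- *Malaise and hematoma cannot be graded.* Malaise can be graded under the open row of Table 5. Hematoma falls to the CTCAE fallback in 9.7.2.
- *The two dose levels cannot be told apart, or the dose effect is exaggerated.* Section 9.5.3.5.1 lists AEs by preferred term and also counts subjects, and 9.5.3.5.3 summarizes blood pressure separately. No hypothesis is tested, no pooled any-event rate is specified, and no calculation shows a distorted dose contrast.
- *Safety holds would be triggered by background readings.* The AE-based holding rules require Grade 3 or higher.

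**Conclusion.** The conflict stands on the text alone. A primary endpoint cites tables whose items do not match the protocol's own solicited list, so some events within 14 days can fall under either of two primary endpoints. The Grade 1 hypertension row and its definition also contradict each other.

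The numerical effect is conditional. Roughly 50–95% of subjects would be flagged after dose 1 with no vaccine effect, but only under the literal reading and the assumed means (112/68 to 125/78) and SDs above. Under the grading-only reading the effect of blood pressure on the solicited endpoint is nil.

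This should be corrected. It concerns how the primary result is defined and reported, and it does not undermine the design. The multiplication of event records is a secondary point that leaves subject-level counts unchanged.

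**What to change.** 1. In 8.2, refer to the 9.7.1 list as the only solicited set, and state that Tables 3–5 are used for grading only. The log for amendment 03 says the 9.7.1 list was brought into line with the diary, which supports using it as the reference.
2. Reconcile the two placements of physical observations in 9.3.3.3, and the Table 4 hypertension row with the definition beneath it. Which version is right is for the sponsor to settle.
3. Report vital signs separately, as change or shift from the pre-dose reading of the same vaccination, and count a Table 4 grade only when it is worse than pre-dose. The readings at 0 h before each dose are already scheduled. The rule should be stated explicitly, because 9.8.1.3 otherwise sets baseline before the first vaccination.
4. In event-count tables, collapse contiguous records of one preferred term after one injection into one event at its maximum grade. Keep the individual records in the listings.

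The cost is protocol wording and short derivation rules for vital signs and event counts, all using data already collected. Reported event rates would be somewhat lower.

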8.3 Secondary Objective

- To evaluate the MVA-MERS-S-specific antibody responses induced by two dosage levels of MVA-MERS-S

8.4 Secondary Endpoints

- Humoral immunity: Magnitude of MERS-S-specific antibody responses as assayed by ELISA

8.5 Exploratory Objectives

- To evaluate MVA-MERS-S-specific cellular immune responses after administration of MVA-MERS-S
- To characterize MERS-S-induced B and T cell memory responses
- To evaluate innate cell subset phenotypes and function induced by MVA-MERS-S
- To evaluate early innate immunity gene expression signatures induced by the MVA-MERS-S
- To comprehensively investigate vaccine-induced humoral immune responses and antibody functions

The results from exploratory objectives may not be part of the final study report.

9 INVESTIGATIONAL PLAN

9.1 Overall Study Design and Plan: Description

This is an open, single-center phase I dose escalation trial in 24 healthy subjects of both sexes. Subjects will be allocated to two different dose cohorts each receiving two vaccine injections, one at day 0 and another on day 28. For safety reasons, subjects will be vaccinated in both cohorts in a staggered manner. Dosing of subjects will commence in dosing cohort 1 (1×10^7 pfu) followed by dosing cohort 2 (1×10^8 pfu). Dosing of cohort 2 will not start before both vaccinations and safety assessments of the first dose cohort are completed.

Second immunization and dose escalation will be performed following a review of the interim safety report by the Local Safety Board.

9.2 Discussion of Study Design, Including the Choice of Control Groups

In close coordination with the national regulatory authorities, the study design, including doses and schedule has been optimized to safely investigate this first-in human vaccine candidate. The study will

be a single center, open label, dose escalation study of the MVA-MERS-S candidate delivered by i.m. injection at two dose levels. In this small study with focus on safety and tolerability, blinding was deferred to ensure maximal safety and transparency.

9.3 Selection of Study Population

24 healthy male and female subjects, aged between 18 and 55 years will be enrolled in this clinical trial. The subjects will be recruited from the study center subject pool and public advertisement. Allocation to a certain treatment number (or subject number) will be done in successive order following screening and based on the subjects' availability.

9.3.1 Inclusion Criteria

The subject must not be enrolled before all inclusion criteria (including test results) are confirmed. Subjects meeting all of the criteria listed below will be included in the study:

1. Ability to understand the subject information and to personally sign and date the informed consent to participate in the study, before completing any study related procedures.
2. Provided written informed consent.
3. Healthy male and female subjects aged 18 – 55 years inclusive at the time of consent. The date of signing informed consent is defined as the beginning of the screening period. This inclusion criterion will only be assessed at the first screening visit.
4. No clinically significant health problems as determined during medical history and physical examination and clinical laboratory results at screening visit. Following laboratory parameters should be within normal limits: WBC, ANC, platelets. AST, ALT and ALP should be \leq ULN, Hb \geq LLN, Troponin T $<$ 2-fold ULN, urine glucose should be negative, CrCL $>$ 60ml/min, urine protein \leq 30mg/dl and total bilirubin should not exceed 1,5 x ULN. Non-clinically significant, minor deviations of laboratory measurements (except for ALT, AST which must be \leq ULN, CrCl which must be $>$ 60ml/min and Troponin T $<$ 2-fold ULN) can be tolerated as long as they will not increase the risk of the individual having an adverse outcome from participating in this study as judged by the investigator. Deviations of laboratory measurements from the reference ranges of more than grade 1 according to Common Toxicity Criteria lead to an exclusion of the subject.
5. Body weight in defined relation to height. Body mass index 18.5 – 30.0 kg/m² and weight $>$ 50 kg at screening.
6. Non-pregnant, non-lactating female with a negative pregnancy test at screening and on day -1/day 27.
7. Females of child-bearing potential who agree to comply with the applicable contraceptive requirements of the protocol (9.3.2.1) from at least 7 days prior to vaccination until day 56 or females who are permanently sterilized (at least 6 weeks post-sterilization).
8. Males who agree to comply with the applicable contraceptive requirements of the protocol as defined above from day 0 through day 56.
9. Be willing to refrain from blood donation during the course of the study.
10. The subject is co-operative and available for the entire study.

Additional criteria for the subjects receiving the 3rd vaccination:

11. Males and females who agree to comply with the applicable contraceptive requirements of the protocol as defined above from day 0 to day 28 of the 3rd vaccination (males) and 7 days prior to 3rd vaccination to day 28 after the 3rd vaccination (females), respectively.
12. Non-pregnant, non-lactating female with a negative pregnancy test on day 0 of the 3rd immunization.

